### 3.3 Primary Endpoint

Procedural time, from trans-septal puncture to attainment of successful PVI. Ablation will be performed as standard procedure with pre-specified ablation technology on the posterior left atrial wall using standard ablation settings.

## 4 STUDY PROTOCOL

### 4.1 Study Design

This study is a prospective, pilot study using the Attune Medical ensoETM esophageal heat transfer device to actively cool the esophagus during RF ablation procedures. This design is appropriate to gather the data needed regarding overall procedural time, compare this to historical controls, and estimate a sample size for a larger study powered for statistical significance.

Once patient consent is obtained, the subject will undergo preparation and anesthesia procedures following standard practice. Once the patient is intubated, the esophageal heat transfer device will be placed into the esophagus according to the IFU. The device will remain in place until the ablation procedure is completed and will be removed before extubation. Posterior left atrial wall ablation using standard parameters will only be performed when the ensoETM has reached a temperature of 4-6°C for at least 2 minutes. The device will be set to neutral or warming temperature (37-42°C) during other aspects of the procedure (such as mapping and anterior wall ablations).

### 4.2 Study Device Description and Intended Use

The ensoETM is a non-sterile multi-lumen silicone tube placed in the esophagus for the purpose of cooling or warming a patient while simultaneously allowing gastric decompression and drainage. Modulation and control of the patient's temperature is achieved by connecting the ensoETM to an external heat exchanger. Two lumens connect to the external heat exchanger, while a third central lumen provides stomach access for connection to a fluid collection device with low intermittent suction

for gastric decompression (Figure 1). The ensoETM is made of standard medical-grade silicone. It is a single-use, disposable, non-implantable device with an intended duration of use of 72 hours or less. Distilled water circulates inside the ensoETM, water does not come into contact with the patient.

[figure not shown]

Figure 1. ensoETM System

Table 1: ensoETM System Components

Diagram Letter	Name	Description
A	ensoETM	ensoETM (ECD-01B or ECD-02B)
B	Tube set connector	Stryker Model 8001-064-035 Insulated Clik-Tite Hose or Cincinnati Sub-Zero connector hose (CSZ P/N 286)
C	Heat exchanger	Stryker Altrix Model 8001 Precision Temperature Management System or Cincinnati Sub-Zero Blanketrol III Hyper-Hypothermia System

The ensoETM has received FDA clearance and its intended use is as a thermal regulating device intended to connect to an external heat exchanger in order to modulate and control patient temperature in the operating room, recovery room, emergency room, or intensive care unit.

#### 4.3 Installation Use and Storage of the Device

Detailed operation of the system is included in the IFU. The ensoETM device should be stored in a dry and clean place and handled according to the IFU. The research team will ensure that the heat exchanger unit will be operated in accordance with the appropriate IFU.

The Company will provide on-site support for training and operation of the ensoETM according to the IFU. As the insertion procedure is similar to placing a standard orogastric tube, it is expected that insertion of the probe and operation of the ensoETM will require limited training and ongoing support, however, the Company will support cases as requested.

#### 4.4 Subject Study Population

Subjects that are indicated for first catheter-based ablation of AF using radiofrequency ablation treatment will be eligible for the study.

#### 4.5 General Inclusion Criteria

Participants must meet all of the following general inclusion criteria:

1. Adult patients (age over 18 years)
2. Undergoing first left atrial ablation for the treatment of atrial fibrillation including pulmonary vein isolation
3. Undergoing catheter-based ablation procedure using radiofrequency energy
4. Patients must be able to understand and critically review the informed consent form.
5. Subjects must understand and agree to study requirements and sign a written informed consent.

#### 4.6 General Exclusion Criteria

Subjects must meet none of the following general exclusion criteria:

1. Patients who are unable to provide informed consent.
2. History of prior AF ablation procedures.
3. Significant co-morbidities that preclude standard ablation procedure.
4. Patients with <40 kg of body mass
5. Patients with relevant esophageal pathology (e.g. esophageal cancer)

### 5 DATA COLLECTION AND MANAGEMENT

#### 5.1 Confidentiality

All parties involved, at all times throughout the clinical investigation shall observe confidentiality of data. All data shall be secured against unauthorized access, and the privacy of each subject and confidentiality of his/her information shall be preserved in reports and when publishing any data. Study subject identification will remain confidential by the assignment and use of study specific identification numbers. All study documentation and/or medical records collected and used for study purposes will be pseudonymised so that an individual subject will not be identified outside the study. Data safety applies to the standard and patient data safety is secured throughout the study. All patients will give informed consent on data safety issues.

#### 5.2 Informed Consent

This study will require subjects to have the ensoETM inserted intra-orally prior to the ablation procedure. As the ensoETM is not routinely used at this Center, detailed information regarding risks are included in the Informed Consent Form presented to subjects enrolling in the study.

This study will require that the operating physician carry out the standard of care for AF ablation. Ultimately, the number and location of ablation lesions and determination of whether to end the procedure will be at the discretion of the operating physician and will be based on the Center's standards as used in recent years. Subjects will be required to sign an Informed Consent Form detailing the potential risks and benefits of their study participation. A study subject can withdraw consent at any time, and for any reason. All patients included will also sign a separate informed consent for AF ablation procedure as standard in the Center.

### 5.3 Data De-Identification

Except where required by law, information shared with persons and organizations outside of the investigational site will not identify the subject by name, government identification number, address, telephone number, or any other direct personal identifier. To ensure that subject identification is kept confidential, a subject's unique identification number will be employed. At the investigational site, a confidential file of informed consent forms and anonymization code numbers will be retained, accessible to the Principal Investigator and/or designee and other authorized personnel. The subject's unique identification number will be employed on all source documentation that is used for data review and analysis.

### 5.4 Data Management

Data entry and development of the primary database of the study will be performed by PI or his designee(s). Data inserted into the database will be reviewed after 10 cases, based on original patient documentation. In case of data queries, PI will resolve based on original patient documentation.

The database is password secured and has an audit trail. Changes to the database can only be made by the delegated study group. Verification of data will be done after 10 cases based on original patient documentation. PI or designee will also be responsible for auditing the database and confirming the overall integrity of the database.

#### 5.4.1 Case Report Forms

The Center will perform primary data collection based on source-documented hospital chart reviews and data transcribed or exported from the mapping and navigation system. Temperature set point and timing will be transcribed and annotated into the mapping software.

Deviations from the study protocol or adverse events will be recorded on the appropriate forms (Deviation / Adverse Event Report). Deviations will be documented, and patients will be excluded from

---

final analysis although deviations will be documented and summarized in final reports. Any deviations that concern patient safety and/or the rights of a study subject will be reported to IRB within 24 hours.

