### 3.2 Study Objective, Hypothesis and Rationale

The objective of this study is to evaluate the impact on procedural efficiency of ablation procedures performed using esophageal heat transfer to cool the esophagus during left atrial RF ablation. This study is designed to measure procedural time of RF ablation to obtain pulmonary vein isolation (PVI) and serve as a pilot to compare to historical controls and enable adequate determination of sample size requirements for a subsequent larger study. The hypothesis is that active esophageal cooling will show a reduced procedural time when compared to standard of care using esophageal temperature monitoring.

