#### 5.4.3 Protocol Deviations and Modifications

Any changes to the approved clinical study must originate from Sponsor in the form of a protocol amendment that must be submitted to the relevant IRB contact. Protocol deviations should be avoided by the PI and site supporting staff. Any deviation from the protocol should be reported to the Sponsor. Any deviation to the clinical study will be reported to the ethical committee in accordance with local requirements. In the situation where deviating from the protocol is in order to protect the life or physical wellbeing of the subjects, which are considered emergency deviations, these should be reported to the Sponsor and Ethical Committee per their local guidelines.

A deviation is any variance from the Investigational Plan requirements (e.g., failure to obtain informed consent, failure to meet inclusion/ exclusion, etc.).

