##### 5.4.4.1 *Sample Size Determination*

As a pilot study, the data obtained will provide information necessary for a formal sample size estimate for a subsequent larger study. A sample size of 20 patients is estimated to be sufficient to provide a 95% confidence interval of +/- 15 minutes around mean procedure duration, assuming a procedure duration of 95 minutes with a standard deviation of 20 minutes.

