## **Evaluable Population**

All enrolled subjects who have received catheter ablation of persistent and paroxysmal atrial fibrillation with complete ablation data and procedural timing will be included in the evaluable population.

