## **Primary Endpoint Analysis**

The primary endpoint of this study will be the total time of active ablation procedure, measured from trans-septal puncture to achievement of PVI. All ablations at posterior left atrial wall during AF ablation are performed under standardized conditions including predefined sets of ablation parameters as per standard of care.

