### *5.4.4.3 Safety Analysis*

All safety-related issues related to the usage of the device will be recorded and documented as **device-related AEs (ADE)**. All safety analyses will be performed on the safety population. No imputation of missing observations will be performed. The Medical Dictionary for Regulatory Activities (MedDRA) version 13.0 or later will be used to code all AEs to a system organ class (SOC) and a preferred term (PT) within the SOC.

The incidence and frequency of AEs will be summarized by system organ class and preferred term for all AEs, device-related AEs (with relationship to study devices and/or study-device-related procedure), serious device-related AEs and device-related AEs leading to study withdrawal and death. The incidence of ADEs will also be tabulated by seriousness, severity, and relationship to study devices and/or procedure.

No AEs will be recorded for study purposes that are not specifically device-related (e.g. arrhythmia recurrences) as this is not within the scope of the study.

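### Section 5.4.1 drops patients with any deviation from the final analysis, the evaluable population keeps them, and the primary endpoint names no set, so the mean can be biased either way if deviations relate to procedure time

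*Combined protocol and SAP*

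**What the plan says.** Section 5.4.1 of the combined protocol and SAP states the rule in one sentence that runs across a page break: "Deviations will be documented, and patients will be excluded from" and then "final analysis although deviations will be documented and summarized in final reports". Section 5.4.3 sets the scope: "A deviation is any variance from the Investigational Plan requirements". Its examples are missing consent and failed eligibility, but the definition has no grading into major and minor.

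The Evaluable Population paragraph under 5.4.4.2 takes in "All enrolled subjects who have received catheter ablation of persistent and paroxysmal atrial fibrillation with complete ablation data and procedural timing". Deviations are not a criterion there.

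The Primary Endpoint Analysis paragraph defines the measure: "The primary endpoint of this study will be the total time of active ablation procedure, measured from trans-septal puncture to achievement of PVI". It names no analysis set. Section 5.4.4.3 does name one for safety: "All safety analyses will be performed on the safety population".

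Section 3.2 says what the result is for: the study is to "serve as a pilot to compare to historical controls and enable adequate determination of sample size requirements for a subsequent larger study".

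**The concern.** Two sections give different answers to who is in the primary analysis, and the paragraph that should settle it is silent. The broad definition in 5.4.3 means that a trivial variance is enough to trigger the exclusion.

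The endpoint is a duration, and deviations during the procedure could be linked to it. An emergency departure from the plan could go with a long case. Not waiting for the cooling condition in 4.1 could go with a short one. Removing such patients afterwards changes the mean for reasons unrelated to the device. That mean is to be set against historical controls, and nothing says that the same exclusion applies to them. The pilot's data are also to inform the size of the next study.

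The rule is also hard to apply uniformly, because who deviates depends on which section is read:

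- **Set-point outside cooling.** The synopsis calls for active warming, gives 40–42°C, and later refers to a nominal setting that it does not define. Section 4.1 gives 37–42°C. Section 6.2 asks for a neutral body temperature without cooling.
- **Prior ablation.** The synopsis excludes earlier AF ablation only if it was in the left atrium. Section 4.6 excludes any earlier AF ablation, and section 4.4 agrees with it.

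**Working it through.** **1. The sections side by side.** All rows concern enrolled, ablated patients.

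| Patient | Evaluable population (5.4.4.2) | Final analysis under 5.4.1 |
|---|---|---|
| No deviation, complete data and timing | in | in |
| One minor variance, complete data and timing | in | **out** |

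The second row is the conflict. No section resolves it. Section 6.6 asks only that deviations be recorded and presented.

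**2. The plan's own precision figure.** Section 5.4.4.1 states: "A sample size of 20 patients is estimated to be sufficient to provide a 95% confidence interval of +/- 15 minutes", assuming a mean of 95 and an SD of 20 minutes. The half-width is t(0.975, n−1) × SD/√n. At n = 20 this is 2.093 × 20/√20 = 9.4 minutes (8.8 with the normal quantile). The stated ±15 is not reproduced, but 20 patients do better than it, so the word sufficient stands. That mismatch is a separate point.

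**3. Deviations unrelated to time.** There is no bias, only fewer patients:

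- n = 18: 2.110 × 20/√18 = 9.9 minutes.
- n = 16: 2.131 × 20/√16 = 10.7 minutes.
- n = 10: 14.3 minutes; n = 9: 15.4 minutes.

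The planned ±15 survives the loss of up to 10 patients. Precision is not the problem.

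**4. Deviations related to time.** Let f be the share excluded and d the mean time of excluded minus retained patients. The mean of all patients is the retained mean plus f × d, so the bias after exclusion is −f × d. With d assumed to be 20 minutes in either direction:

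- 2 of 20 excluded: 0.10 × 20 = 2.0 minutes, down if the excluded cases are longer, up if shorter.
- 4 of 20 excluded: 0.20 × 20 = 4.0 minutes, likewise.

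**5. Illustration with a graded link.** The documents give no deviation rate or pattern, so both are assumed: 10–20% deviate, with the odds of deviating multiplied (or divided) by 2 to 5 per SD of time. Times have mean 95 and SD 20, either normal or lognormal. Shifts and SDs come from 4,000,000 simulated draws. Coverage of the t-based 95% interval comes from 300,000 simulated trials of 20.

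| Times | Cases mainly lost | Shift in mean (min) | SD | Coverage |
|---|---|---|---|---|
| Normal | slow (fast mirrors it) | −1.3 to −4.7 | 19.6 to 17.9 | 94% to 84% |
| Lognormal | slow | −1.5 to −5.2 | 19.0 to 16.2 | 92% to 76% |
| Lognormal | fast | +1.2 to +4.1 | 20.1 to 19.3 | 95% to 90% |

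If instead the middle 10–20% of times were lost, the mean would move by at most 0.5 minutes and the SD would rise to between 21.1 and 22.3. For scale, the standard error of the mean is 20/√20 = 4.5 minutes. Sampling error alone puts the 95% interval for an SD of 20 at 15.2 to 29.2.

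**6. Size of the next study.** Required n is proportional to SD²/difference². Take normal times, 20% deviating and odds ×2 per SD, which gives SD 19.36 and a shift of 2.58 minutes.

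- Fixed target difference: (19.36/20)² = 0.937, about 6% too small. If the middle 20% were lost instead: (22.32/20)² = 1.25, about 25% too large.
- Sized on the observed difference, with true difference D: 0.937 × (D/(D + 2.58))² if slow cases are lost, and 0.937 × (D/(D − 2.58))² if fast cases are lost.

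| Assumed D (min) | Slow cases lost | Fast cases lost |
|---|---|---|
| 10 | 41% too small | 70% too large |
| 15 | 32% too small | 37% too large |
| 30 | 21% too small | 12% too large |

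The documents do not give the historical-control mean, so D is unknown and no single value can be quoted.

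**The case against.** **The evaluable population is obviously meant.** It is defined just above the primary endpoint paragraph, so this is the natural inference. It does not remove the conflict, because 5.4.1 speaks of the final analysis without qualification.

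**An on-protocol estimate is defensible in a single-arm pilot.** This stands in part. The documents compel only that the two sections agree and that the set be named; grading deviations beforehand would also achieve that. Keeping all evaluable patients is preferred because membership then does not turn on a judgement that could be made once times are known.

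**The exclusions would be visible.** This stands as mitigation. Sections 5.4.1 and 6.6 require deviations to be reported, 5.4.4 promises patient listings, and 6.6 bars non-emergency deviations without prior written approval. A reader might redo the analysis, but the headline mean would still be the selected one.

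**The shifts are small.** Most illustrated shifts lie below or near the standard error of 4.5 minutes, and all are well inside ±15. This limits the weight of the point. Bias is nevertheless not reflected in the interval, as the coverage figures show.

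**The evaluable definition has its own gap.** It does not require that the device was placed or working, although section 8.4 foresees failures and malfunctions. This stands and is taken into the fix.

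Stronger readings that a reader might infer are not supported:

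- *The rule will make cooling look faster, or leave the next study too small.* The documents give no pattern of deviations, and both directions are possible.
- *No setting satisfies both the synopsis and 6.2, so every patient could be excluded.* That needs a strict reading of neutral, which 6.2 itself explains as no cooling, and it overlooks the synopsis's undefined nominal setting. The wording is inconsistent, but no more than that is shown.
- *Safety results are affected.* Section 5.4.4.3 already assigns them to the safety population.

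**Conclusion.** The conflict is certain from the text: a patient with complete timing and any variance is kept by 5.4.4.2 and removed by 5.4.1, and the primary endpoint paragraph does not choose between them. The consequence is conditional. It is nil for bias, and slight for precision, if deviations are unrelated to procedure time. Otherwise the bias can go in either direction: about 1 to 5 minutes in the mean, with coverage between 95% and 76%, under rates, odds and distribution shapes that are all assumed. The effect on the next study's size has no fixed direction. This should be fixed before analysis. It does not invalidate the pilot.

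**What to change.** - Delete the exclusion in 5.4.1; keep the requirement to document and summarise deviations.
- In 5.4.4.2 and in the primary endpoint paragraph, name the evaluable population as the primary set and state that patients with deviations stay in it.
- State beforehand, without reference to procedure time, whether patients ablated with the device not placed or not working count in the primary set, and report their number.
- List all deviations, and give one deviation-free analysis as sensitivity only.
- State how data are handled after a patient withdraws consent, which 5.2 allows at any time.
- State that the safety population is unchanged.
- So that deviations are identified the same way in every case, reconcile the set-point wording outside cooling (synopsis, 4.1, 6.2) and the prior-ablation exclusion (synopsis against 4.4 and 4.6). This review takes no position on which version is right.

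The timing of cooling start and the handling of cases without PVI are separate points.

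The cost is wording in three places, the reconciliations above, and one sensitivity table; no added patients or data. The downside is that the primary set will include some cases not done exactly to plan.

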#### 5.4.2 Monitoring Plan

The investigator and research team will allocate adequate time for monitoring activities and monitoring of all data will be performed on a regular basis throughout the study. For monitoring access to all the above noted study-related documents and study related facilities (e.g. clinical EP laboratories) will be granted. Monitoring will be performed by a committee not involved in the study conduct.

#### 5.4.3 Protocol Deviations and Modifications

Any changes to the approved clinical study must originate from Sponsor in the form of a protocol amendment that must be submitted to the relevant IRB contact. Protocol deviations should be avoided by the PI and site supporting staff. Any deviation from the protocol should be reported to the Sponsor. Any deviation to the clinical study will be reported to the ethical committee in accordance with local requirements. In the situation where deviating from the protocol is in order to protect the life or physical wellbeing of the subjects, which are considered emergency deviations, these should be reported to the Sponsor and Ethical Committee per their local guidelines.

A deviation is any variance from the Investigational Plan requirements (e.g., failure to obtain informed consent, failure to meet inclusion/ exclusion, etc.).

#### 5.4.4 Data Analysis and Acceptance

All analyses will be performed using validated statistical software. In general, the study endpoints will be assessed relative to the study objectives. Patient data listings and tabular and graphical presentations of baseline and operative characteristics and outcome results will be created.

